2.3. Pooling Algorithm for Analysis Centers

For efficacy analyses, investigator sites may be pooled as a stratification factor if there are sites with less than 10 subjects randomized. Sites with small number of subjects randomized will be pooled with the sites with larger number of randomized subjects by similar region/location when appropriate, so the number of subjects within the aggregated sites is at least 10. Note that site size and geography were considered when aggregating site sizes. Specific pooling strategy can be found in [Attachment 1](#).

2.4. Analysis Sets

2.4.1. Efficacy Analysis Set

2.4.1.1. Full Analysis Set

For the efficacy analyses in this study, the full analysis set (FAS) will be used according to subjects' assigned treatment to which they were randomized, regardless of the treatment they actually received. The FAS includes all randomized subjects. The full analysis set will be used for all primary and secondary efficacy analyses. In addition, for endpoints that include a non-inferiority test, analyses will also be performed using the per protocol analysis set as defined below.

2.4.1.2. Per Protocol Analysis Set

The per protocol population includes subjects in full analysis set except those

- who did not meet the inclusion criteria 3, 4 or 5 in the protocol as listed below:
 - Have a PASI ≥ 12 at screening and at baseline.
 - Have an IGA ≥ 3 at screening and at baseline.
 - Have an involved BSA $\geq 10\%$ at screening and at baseline.
- who violated the exclusion diagnosis criteria 7 or 8:
 - Has a nonplaque form of psoriasis (eg, erythrodermic, guttate, or pustular).
 - Has current drug-induced psoriasis (eg, a new onset of psoriasis or an exacerbation of psoriasis from beta blockers, calcium channel blockers, or lithium).
- who violated the concomitant or previous psoriasis medications or therapies-related exclusion criteria (12, 13, and 15 through 22) as listed below:
 - Has previously received guselkumab or secukinumab.
 - Has any contraindications to the use of secukinumab per local prescribing information.
 - Has received any anti-tumor necrosis factor α biologic therapy within 3 months before the first administration of study drug.

- Has received any therapeutic agent directly targeted to IL-12, IL-17A, IL-17R, or IL-23 within 6 months of the first administration of study drug (including but not limited to ustekinumab, tildrakizumab [MK3222], risankizumab [BI-655066], ixekizumab [LY2439821], or brodalumab [AMG 827]) with the exception of secukinumab (which is completely excluded).
- Has received natalizumab, belimumab, or agents that modulate B cells or T cells (eg, rituximab, alemtuzumab, abatacept, or visilizumab) within 12 months of the first administration of study drug.
- Has received any systemic immunosuppressants (eg, methotrexate [MTX], azathioprine, cyclosporine, 6-thioguanine, mercaptopurine, mycophenolate mofetil, tacrolimus) or anakinra within 4 weeks of the first administration of study drug.
- Has received phototherapy or any systemic medications/treatments that could affect psoriasis or IGA evaluations (including, but not limited to, oral or injectable corticosteroids, retinoids, 1,25-dihydroxy vitamin D3 and analogues, psoralens, sulfasalazine, hydroxyurea, fumaric acid derivatives, herbal treatments, or traditional Taiwanese, Korean, or Chinese medicines) within 4 weeks of the first administration of study drug.
- Has used topical medications/treatments that could affect psoriasis or IGA evaluations (including, but not limited to, corticosteroids, anthralin, calcipotriene, topical vitamin D derivatives, retinoids, tazarotene, methoxsalen, trimethylpsoralens, pimecrolimus, tacrolimus, or topical traditional Taiwanese, Korean, or Chinese medicines) within 2 weeks of the first administration of study drug.
- Is currently receiving lithium, antimalarials, or intramuscular (IM) gold, or have received lithium, antimalarials, or IM gold within 4 weeks of the first administration of study drug.
- Has received an experimental antibody or biologic therapy within the previous 6 months, or received any other experimental therapy or new investigational agent within 30 days or 5 half-lives (whichever is longer) of any study drug administration or is currently enrolled in another study using an investigational agent or procedure.
- who did not complete the specified exposure to study agent as outline below
 - subjects randomized to guselkumab at Week 0 but did not receive all scheduled guselkumab administrations, received one or more extra guselkumab administrations, or received one or more secukinumab administrations prior to the specified time period for the endpoints (eg, Week 12 or Week 48).
 - subjects randomized to secukinumab at Week 0 but did not receive all scheduled secukinumab administrations, received one or more extra secukinumab administrations, or received one or more guselkumab administrations prior to the specified time period for the endpoints.

However, for those who did not complete the specified exposure to study agent as outline above, subjects who discontinued the study agent due to unsatisfactory therapeutic effect or an adverse event (AE) of worsening of psoriasis, or subjects who started prohibited medications and continued receiving study agents prior to the specified timepoint for the endpoints will be

included in the per protocol analysis and the treatment failure rules specified in Section 5.1.3.2 will apply.

Subjects who were excluded from the per protocol analyses will also be summarized.

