6. DOSAGE AND ADMINISTRATION

A 100 mg/mL solution of guselkumab in a single-use prefilled syringe (PFS) assembled with the UltraSafe PLUS™ Passive Needle Guard (PFS-U) device will be used. Subjects who are randomized to the guselkumab treatment arm will receive 2 injections: 1 injection of active guselkumab and 1 injection of placebo when guselkumab is scheduled to be administered (Weeks 0, 4, 12, 20, 28, 36, 44) or 2 injections of placebo when no guselkumab is scheduled to be administered (Weeks 1, 2, 3, 8, 16, 24, 32, and 40). The purpose of administering 2 injections is to mimic the 2 injections required for each secukinumab dose, and to thus maintain the blind. Commercially available secukinumab (Cosentyx) will be supplied as a single-use PFS and administered according to the manufacturer's directions. Each 300 mg dose is given as 2 SC injections of 150 mg each. An appropriately qualified, unblinded member of the study staff will administer the drug and will have no other role in the conduct of the study.

All study drug injections will be administered at the investigational site. With the exception of the unblinded site personnel who dispense and/or administer the investigational product, all other site personnel and subjects will remain blinded to the treatment assignments until the last subject completes Week 56 evaluations and the database has been locked. Sites must ensure that they have the ability to physically blind and/or separate the blinded subject from the unblinded administrator. A physical barrier must be used such that the study drug can be administered by the unblinded site personnel, and the subject and other site personnel remain blinded.

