1.2. Trial Design

This is a Phase 3, randomized, double-blind, multicenter, active-comparator-controlled study in subjects with moderate to severe plaque-type psoriasis. The target population is adult men or women, with a diagnosis of plaque-type psoriasis (with or without PsA) for at least 6 months before the first administration of study drug. Subjects must have moderate to severe plaque-type psoriasis defined by IGA ≥ 3 , PASI ≥ 12 , and involved body surface area (BSA) $\geq 10\%$. Subjects must be candidates for either systemic therapy or phototherapy for psoriasis, and may have previously received some systemic therapies or phototherapy for psoriasis. Subjects with nonplaque forms of psoriasis (eg, erythrodermic, guttate, or pustular) or with drug-induced psoriasis (eg, a new onset of psoriasis or an exacerbation of psoriasis from beta blockers, calcium channel blockers, or lithium) are excluded. Subjects who have ever received guselkumab or secukinumab are also excluded.

Key features of study drug administration for each treatment group are outlined below.

Week 0 through Week 44 (Blinded Treatment Period)

As depicted in [Figure 1](#), approximately 1,040 subjects who satisfy all inclusion and exclusion criteria will be randomized in a 1:1 ratio to 1 of 2 treatment arms:

- **Group I** (n=520): guselkumab 100 mg SC at Weeks 0, 4, 12, and q8w thereafter through Week 44.
- **Group II** (n=520): secukinumab 300 mg SC at Weeks 0, 1, 2, 3, 4 and q4w thereafter through Week 44.

[figure not shown]
After Week 44 through Week 56 (Follow-up Period)

The follow-up period will begin after Week 44 and extend through Week 56.

There is one database locks (DBL) in this study at Week 56. The Sponsor, the investigators, subjects, and site monitors will be unblinded after the Week 56 DBL has occurred. The end of the study is defined as the timepoint when the last subject completes the Week 56 visit.

A diagram of the study design is provided in [Figure 1](#).

Figure 1: Schematic Overview of the Study

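### SAP 2.4.1.2 counts only active doses as per-protocol exposure, so missing any of eight of the 15 blinded dosing visits excludes a secukinumab subject but keeps a guselkumab subject

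*SAP*

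**What the plan says.** SAP 2.4.1.2 drops from the per-protocol set "subjects randomized to guselkumab at Week 0 but did not receive all scheduled guselkumab administrations" and, separately, "subjects randomized to secukinumab at Week 0 but did not receive all scheduled secukinumab administrations". Doses count only if they fall "prior to the specified time period for the endpoints (eg, Week 12 or Week 48". An exception keeps "subjects who discontinued the study agent due to unsatisfactory therapeutic effect or an adverse event (AE) of worsening of psoriasis", and also keeps subjects who started prohibited medication but stayed on study agent; the treatment failure rules then apply to them. Neither the rule nor the exception mentions placebo injections. Excluded subjects are to be summarized, but a breakdown by arm and reason is not specified.

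Protocol Section 6 gives the guselkumab arm one active and one placebo injection "when guselkumab is scheduled to be administered (Weeks 0, 4, 12, 20, 28, 36, 44", and "2 injections of placebo when no guselkumab is scheduled to be administered (Weeks 1, 2, 3, 8, 16, 24, 32, and 40". The other arm receives "secukinumab 300 mg SC at Weeks 0, 1, 2, 3, 4 and q4w thereafter through Week 44" (SAP 1.2).

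SAP 2.4.1.1 makes the full analysis set the basis of all primary and secondary efficacy analyses and adds that "for endpoints that include a non-inferiority test, analyses will also be performed using the per protocol analysis set". SAP 5.2.7, 5.3.2 and 5.4.2 repeat this for the primary, major secondary and other secondary endpoints. Under SAP 5.1.3.3, missing binary outcomes become non-response.

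**The concern.** Subjects are blinded and have the same visit schedule in both arms. At eight of the visits, the same missed visit leads to different per-protocol status depending only on the arm. The secukinumab set is filtered on attendance at 15 visits and the guselkumab set on attendance at seven. If attendance is related to response, the filtering itself produces a difference between arms that the drugs did not cause.

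Part of the effect needs no such relation. Suppose a guselkumab subject skips Week 24, 32 or 40 altogether. That subject stays in the set and is imputed as a non-responder for PASI 90 at all seven visits from Week 24 to Week 48, while the matching secukinumab subject is removed. The same happens at Week 16 for PASI 90 at both Week 16 and Week 48.

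For PASI 90 and PASI 75 at Week 12, non-inferiority is the only planned test, and there the ratio of scheduled doses is widest. What is at stake is how a reader interprets agreement or disagreement between the per-protocol and full-analysis-set results.

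**Working it through.** **1. The plan's own figures.** The documents state no per-protocol count or exclusion rate. The nearest stated figure is Table 1: 60% v 70% with 520 per arm. With the pooled variance under the null, √(2 × 0.65 × 0.35 / 520) = 0.02958; unpooled, √((0.24 + 0.21) / 520) = 0.02942. Power = Φ((0.10 − 1.96 × 0.02958) / 0.02942) = Φ(1.43) = 92.3%, against the stated 92%. The sample-size inputs used in step 6 are therefore consistent with the plan.

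**2. Dose counts** (Protocol Section 6; SAP 1.2). Assessments precede dosing at a visit (Time and Events Schedule, footnote c), so a dose on the endpoint day does not count as prior exposure.

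| Endpoint week | Guselkumab doses that count | Secukinumab doses that count |
|---|---|---|
| 12 | 2 (Weeks 0, 4) | 6 (Weeks 0–4, 8) |
| 16 | 3 | 7 |
| 48 | 7 | 15 |

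The eight extra secukinumab visits are exactly the eight placebo-only guselkumab visits. Leaving out Week 0, the randomization visit, Week 48 is 14 v 6.

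**3. Which patterns are affected.** For Week 48 endpoints, only intermittent misses at those eight visits. A permanent stop before Week 44 that falls outside the exception misses the Week 44 active dose in either arm and excludes the subject in both. For Week 12 endpoints, a stop for a non-efficacy reason after the Week 4 dose and before the Week 8 dose excludes only secukinumab subjects.

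**4. Expected exclusions and shift.** Assumption: each visit is missed independently with probability q, the same in both arms. The documents give no value, so a range is shown.

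- Excluded = 1 − (1 − q)^k, with k from step 2.
- Share of the guselkumab Week 48 set that missed at least one placebo-only visit = 1 − (1 − q)^8.
- Last column: that share × −20 points, assuming such subjects respond 20 points less often.

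| q | Week 48: gus v sec | Week 12: gus v sec | Placebo-visit missers kept in gus set | Shift in difference, Week 48 (points) |
|---|---|---|---|---|
| 0.25% | 1.7% v 3.7% | 0.5% v 1.5% | 2.0% | −0.4 |
| 0.5% | 3.4% v 7.2% | 1.0% v 3.0% | 3.9% | −0.8 |
| 1% | 6.8% v 14.0% | 2.0% v 5.9% | 7.7% | −1.5 |
| 2% | 13.2% v 26.1% | 4.0% v 11.4% | 14.9% | −3.0 |
| 3% | 19.2% v 36.7% | 5.9% v 16.7% | 21.6% | −4.3 |
| 5% | 30.2% v 53.7% | 9.8% v 26.5% | 33.7% | −6.7 |

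A two-class version lets misses cluster. Let 20% of subjects miss 10% of visits and respond 20 points less often, while the rest miss 1%. Poor attenders then make up:

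- guselkumab: 0.2 × 0.9^7 / (0.2 × 0.9^7 + 0.8 × 0.99^7) = 0.0957 / 0.8413 = 11.4%
- secukinumab: 0.2 × 0.9^15 / (0.2 × 0.9^15 + 0.8 × 0.99^15) = 0.0412 / 0.7292 = 5.6%

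Two equally effective arms would differ by (0.114 − 0.056) × −20 ≈ −1.1 points. With 15% of visits missed and a 30-point deficit, the shift is −1.6 points.

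**5. The imputation route.** For PASI 90 at all seven visits, the share of retained guselkumab subjects who miss Week 24, 32 or 40 is 1 − (1 − q)^3: 3.0% at q = 1% and 5.9% at q = 2%. If the whole visit is missed, each is an automatic non-responder. The resulting shift is at most that share, because some would not have responded anyway.

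**6. Cost of equal rules.** With true rates of 65% in both arms and q = 1%, the present rule leaves 485 v 447 subjects. Standard error = √(0.2275 × (1/485 + 1/447)) = 0.0313, and non-inferiority power = Φ(0.10/0.0313 − 1.96) = 89.2%. Counting all 15 visits in both arms leaves 447 v 447; the standard error is 0.0319 and power is 88.0%.

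**The case against.** The rule has a sound pharmacological reading. It sits under completion of the specified exposure to study agent. A guselkumab subject who misses a placebo-only visit has had every guselkumab dose; a secukinumab subject who misses that visit is under-dosed. Equal behaviour is not equal exposure, and an attendance rule would discard fully dosed guselkumab subjects. This stands, and it is why the present version should be kept rather than replaced.

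The size may also be small. Dosing is at the site under staff control (Protocol Section 7), and the exposure rule sets no dosing window, so a late dose can still count as received. At q of 0.5% or less, the shift in step 4 is under one point against a 10-point margin. This stands too, but without a documented missed-visit rate it cannot be relied on.

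An imbalance would be partly visible, since exclusions and study-agent compliance (SAP 4.3) are summarized. That reveals unequal selection but does not correct it.

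A reader might also infer that the exclusion list is open to manipulation because it depends on the treatment codes. The documents do not support this: the rule is prespecified and mechanical, and the wrong-drug exclusions need the codes under any version.

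**Conclusion.** The asymmetry is real, and nothing elsewhere in either document removes it: 15 v 7 scheduled doses for Week 48 endpoints (14 v 6 without the randomization visit) and 6 v 2 for Week 12. The two per-protocol arms are selected by unequal rules on post-randomization behaviour, and two other secondary endpoints are affected directly through non-responder imputation.

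The size cannot be determined. The figure of 6.8% v 14.0% excluded holds only for an independent 1% miss rate per visit, equal in both arms. That secukinumab loses about twice as many subjects is a result of this model, not a fact in the documents.

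Two stronger readings are tempting and not supported:

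- **That the rule could manufacture non-inferiority.** If those who miss visits respond worse, or are imputed as non-responders, the bias runs against guselkumab. The opposite direction needs poor attenders to respond better, for which the documents offer no basis. The practical risk is a spurious disagreement between the two analysis sets.
- **That the confirmatory conclusions are compromised.** The full analysis set decides the primary and all sequential tests, and no step depends on the per-protocol result. Type I error is unaffected.

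This is a worthwhile correction to a supportive analysis, not a defect in the main inference.

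**What to change.** In SAP 2.4.1.2, add a second, treatment-neutral per-protocol analysis for every endpoint with a non-inferiority test. In both arms, and subject to the existing exceptions, it excludes subjects who missed any scheduled study-agent administration, active or placebo, before the endpoint. The wrong-drug, extra-dose and eligibility exclusions stay as they are. Keep the active-exposure version alongside it, and report exclusions from both versions by arm and reason.

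This equalizes expected exclusion from missed visits when the arms miss visits at the same rate. It also closes the Week 16, 24, 32 and 40 imputation route and the Week 4-to-8 stop, because those guselkumab subjects would now be excluded too.

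The cost is SAP wording, one derived flag and one further display. Missed administrations are already recorded (Protocol Section 7), and the protocol's statistical section defines no per-protocol set, so only the SAP changes. The added set holds somewhat fewer guselkumab subjects: under the step 6 assumptions, 447 instead of 485, with non-inferiority power of about 88.0% instead of 89.2%.

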8. CONCOMITANT THERAPY

Concomitant therapies must be recorded throughout the study from screening and continuing until 12 weeks after the last dose of study drug for randomized subjects. Concomitant therapies should also be recorded beyond Week 56 only in conjunction with SAEs that meet the criteria outlined in Section 12.3.2. Serious Adverse Events.

All therapies (prescription or over-the-counter medications, including vaccines, vitamins, herbal supplements) different from the study drug, as well as all shampoos used to treat psoriasis, moisturizers, or emollients, must be recorded in the eCRF. Modification of an effective preexisting therapy should not be made for the explicit purpose of entering a subject into the study.

If a prohibited therapy is administered during the blinded active treatment phase (ie, Week 0 to Week 44 - unless agreed to by the medical monitor), the subject should be discontinued from study treatment. If a prohibited therapy is initiated during the safety follow-up period (Week 48 to Week 56), the subject should still complete his or her final study visit at Week 56, and the medication should be recorded as a concomitant medication.

The sponsor must be notified in advance (or as soon as possible thereafter) of any instances in which prohibited therapies are administered.

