10.2. Discontinuation of Study Treatment/Withdrawal from the Study

Discontinuation of Study Treatment

A subject will not be automatically withdrawn from the study if he or she has to discontinue treatment before the end of the treatment regimen.

A subject's study treatment must be discontinued if:

- The investigator believes that for safety reasons or tolerability reasons (eg, AE) it is in the best interest of the subject to discontinue study treatment
- The subject becomes pregnant
- The subject is diagnosed with a malignancy, with the exception of no more than 2 localized basal cell skin cancers that are treated with no evidence of recurrence or residual disease.
- The subject is deemed ineligible according to the following TB screening criteria:
 - A diagnosis of active TB is made.
 - A subject has symptoms suggestive of active TB based on follow-up assessment questions and/or physical examination, or has had recent close contact with a person with active TB, and cannot or will not continue to undergo additional evaluation.

- A subject undergoing evaluation has a chest radiograph with evidence of current active TB and/or a positive QuantiFERON-TB Gold test result and/or an indeterminate QuantiFERON-TB Gold test result on repeat testing (refer to Section 9.6) (and/or a positive tuberculin skin test result in countries in which the QuantiFERON-TB Gold test is not approved/registered or the tuberculin skin test is mandated by local health authorities). Indeterminate QuantiFERON-TB Gold test results should be handled as described in Section 9.6.
- A subject receiving treatment for latent TB discontinues this treatment prematurely or is noncompliant with the therapy.
- The subject initiates a protocol-prohibited medication, eg, for a worsening of his or her psoriasis (unless agreed to by the medical monitor).
- The subject withdraws consent for administration of study drug.
- The subject is unable to adhere to the study visit schedule or comply with protocol requirements.
- The subject develops an allergic reaction such as bronchospasm with wheezing and/or dyspnea requiring ventilatory support, or symptomatic hypotension that occurs following a study drug administration.

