- The subject has a reaction resulting in myalgia and/or arthralgia with fever and/or rash (suggestive of serum sickness and not representative of signs and symptoms of other recognized clinical syndromes) occurring 1 to 14 days after an injection of study drug. These may be accompanied by other events including pruritus, facial, hand, or lip edema, dysphagia, urticaria, sore throat, and/or headache.
- Discontinuation of study treatment should be considered for subjects who report suicidal ideation with intention to act (“4”), suicidal ideation with specific plan and intent (“5”), or a suicide attempt (interrupted suicide attempt, aborted suicide attempt, or preparatory behaviors for making a suicide attempt) on a postbaseline eC SSRS assessment. Discussion of such subjects with the medical monitor or designee is required.
- Discontinuation of study treatment should be considered for subjects who develop a serious or opportunistic infection. Discussion of such subjects with the medical monitor or designee should also be considered.

Subjects who decide to discontinue study drug administration must be interviewed by the investigator to determine if a specific reason for discontinuing study drug can be identified. Subjects should be explicitly asked about the possible contribution of AEs to their decision to discontinue study drug; investigators should confirm that any AE information elicited has been documented. If the subject elects to discontinue study drug due to an AE, the event should be recorded as the reason for study drug discontinuation, even if the investigator’s assessment is that the AE would not require study drug discontinuation. The reason for study drug discontinuation must be documented in the eCRF and in source documents. Study drug assigned to a subject who discontinues may not be assigned to another subject.

If the subject discontinues study treatment before his or her last scheduled injection, he or she should return for the remaining regularly scheduled study visits for at least 12 weeks after receiving the last administration of study drug. For subjects who complete their final study visit prior to Week 48, every effort should be made to conduct the Week 48 assessments as indicated in the Time and Events Schedule. For subjects who discontinue from the study prior to Week 48, serum is not to be collected for measurement of biomarkers.

Withdrawal From the Study

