5.1.3.1. Treatment Failure Criteria

Subjects who discontinue study agent due to lack of efficacy, an adverse event (AE) of worsening of psoriasis, or who started a protocol-prohibited medication/therapy during the study that could affect their psoriasis are considered as treatment failures.

The protocol-prohibited medications/therapies include:

Topical Therapies:

- Any topical therapies used for psoriasis (with the exception of topical moisturizers and shampoos containing tar or salicylic acid only)

Phototherapy or Systemic Therapies:

- Any systemic corticosteroid used for psoriatic arthritis or psoriasis with the exception of intra-articular corticosteroids.
- Any other anti-psoriatic systemic therapy or biologic therapy.
- Phototherapy of UVB or PUVA.
- Any other phototherapy for psoriasis.

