5.1.3.2. Treatment Failure Rules

A subject who meets one or more of the treatment failure criteria specified in Section 5.1.3.1 will be considered a treatment failure from that point onward. The baseline values will be used for all directly measured endpoints regardless of the actual measurements. Zero will be assigned to improvement and percent improvement, and non-responder status will be assigned to binary response variables.

Treatment failure is assumed to have occurred at the earlier of the following dates:

- Date of discontinuation (DC) of study treatment due to lack of efficacy or an AE of worsening of psoriasis or
- Date of initiation of a protocol-prohibited medication/therapy during the study that could improve psoriasis

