5.2.4. Data Handling

Subjects who meet treatment failure criteria specified in Section 5.1.3.1 prior to Week 48 will be considered PASI 90 nonresponders at Week 48. In addition, subjects with a missing PASI score at Week 48 or who do not return for evaluation at Week 48 will be considered PASI 90 nonresponders at Week 48.

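### The per-protocol set drops subjects taken off study agent for starting prohibited medication, although the full analysis set counts them as nonresponders

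*SAP*

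**What the plan says.** The SAP builds the per-protocol set by exclusion. Under Section 2.4.1.2, a subject who missed any scheduled administration of the assigned drug before the endpoint is removed. Two groups are then restored, with the Section 5.1.3.2 failure rules applied to them:

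- subjects who stopped study agent for unsatisfactory effect or an adverse event of worsening psoriasis;
- "subjects who started prohibited medications and continued receiving study agents prior to the specified timepoint".

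The failure rules carry no such condition about continuing. SAP 5.1.3.1 covers subjects "who started a protocol-prohibited medication/therapy during the study that could affect their psoriasis are considered as treatment failures". SAP 5.1.3.2 lists as a failure date the "Date of initiation of a protocol-prohibited medication/therapy during the study that could improve psoriasis". SAP 5.2.4 adds: "Subjects who meet treatment failure criteria specified in Section 5.1.3.1 prior to Week 48 will be considered PASI 90 nonresponders at Week 48".

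The protocol says what normally happens to these subjects. If prohibited therapy is given between Week 0 and Week 44, Protocol 8 says "the subject should be discontinued from study treatment", unless the medical monitor agrees otherwise. Protocol 10.2 lists this as a separate ground for mandatory discontinuation: "The subject initiates a protocol-prohibited medication, eg, for a worsening of his or her psoriasis (unless agreed to by the medical monitor").

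On the use of the set, SAP 2.4.1.1 says that for endpoints with a non-inferiority test, "analyses will also be performed using the per protocol analysis set".

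**The concern.** The exception and the failure rule it invokes do not match. The second restored group consists of subjects who stayed on study agent, which the protocol allows only with the medical monitor's agreement. Subjects handled by the protocol's default rule fall outside both groups and are dropped.

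Whether a given failure counts as a nonresponder or disappears can then turn on the recorded reason for stopping. A subject who flares, takes a prohibited drug and is stopped stays in if the reason is lack of effect, and goes out if it is prohibited medication.

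Everyone lost through this gap is a nonresponder by rule, so the exclusion is made after randomization and depends on outcome. It can shift the per-protocol difference in either direction. A discrepancy between the FAS and per-protocol results, normally read as information about adherence, could come from this clause.

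**Working it through.** **Tracing one subject.** Take a subject who starts a systemic antipsoriatic drug at Week 22, is stopped under Protocol 10.2 with prohibited medication as the reason, and misses later doses.

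| Step | FAS | Per-protocol set |
|---|---|---|
| Failure rule (SAP 5.1.3.1, 5.1.3.2) | Failure from Week 22 | Reached only if retained |
| Exposure rule (SAP 2.4.1.2) | Not applied | Excluded for missed doses |
| Exception, first group | Not applicable | Not met: different reason for stopping |
| Exception, second group | Not applicable | Not met: study agent not continued |
| PASI 90 at Week 48 | Nonresponder | Not counted |

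The gap is confined to such cases. Subjects stopped for lack of effect or worsening psoriasis are kept, as are those continued with the medical monitor's agreement. So are those who had every scheduled dose before the endpoint, for example a subject who starts the therapy after Week 44.

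**Inputs.** From SAP 1.4 and 5.1.1: 520 subjects per arm, a 10-point margin and one-sided alpha of 0.025. The plan's own power figures are not in dispute and reproduce: for PASI 90 at 60 vs 70%, 65 vs 75% and 70 vs 80%, a pooled-variance normal approximation gives 92.3%, 94.2% and 96.2%, against 92%, 94% and 96% in Table 1.

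The share *d* of an arm lost through the gap is not in the documents. I assume 1% to 3%, about 5 to 16 of 520.

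**Formulas.** The dropped subjects are all nonresponders, so the per-protocol rate is p/(1 - d) on n = 520(1 - d). With D the difference in points, guselkumab minus secukinumab, the chance that the lower 95% bound is at or above -10 is P(Z > 1.96 - (D + 10)/SE). This is an unstratified normal approximation that ignores site strata.

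**True FAS difference exactly at the margin (guselkumab 60%, secukinumab 70%).** For the 3%/1% split: 0.60/0.97 = 61.86% and 0.70/0.99 = 70.71%, so D = -8.85 with SE 2.95. Then 1.96 - 1.15/2.95 = 1.57, and the chance is 5.8%.

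| Dropped, guselkumab / secukinumab | D (points) | Chance of clearing -10 |
|---|---|---|
| 0% / 0% | -10.00 | 2.5% |
| 1% / 1% | -10.10 | 2.3% |
| 2% / 2% | -10.20 | 2.1% |
| 3% / 3% | -10.31 | 2.0% |
| 2% / 1% | -9.48 | 3.7% |
| 1% / 2% | -10.82 | 1.3% |
| 3% / 1% | -8.85 | 5.8% |
| 1% / 3% | -11.56 | 0.6% |

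**Equal rates of 65%.** A 3%/1% split gives 67.01 - 65.66 = +1.35 points; the reverse gives -1.35.

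**A result that changes sides.** With observed FAS rates of 60% and 65%, D is -5.0 and the lower bound is -10.9, which fails. If 3% and 1% are dropped, D is -3.8 and the lower bound is -9.7, which passes.

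**Arm-neutral dropping cannot be presumed at Week 12.** Before Week 12, guselkumab is due at Weeks 0 and 4, while secukinumab is also due at Week 8. Exposure is judged on each arm's own active doses. A subject stopped for prohibited medication after the Week 4 dose and before Week 8 is therefore dropped on secukinumab but kept as a nonresponder on guselkumab. For the Week 12 endpoints this works against guselkumab.

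**The case against.** The best case for leaving the text alone has five parts.

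- **Intent.** No passage says that every treatment failure should be kept. The SAP amendment revisited the per-protocol exposure definition, and dropping subjects who stopped drug and switched therapy is a defensible per-protocol choice. But Section 2.4.1.2 itself invokes the failure rules for subjects with incomplete exposure, and it keeps prohibited-medication users who stay on study agent. Dropping those who were stopped as the protocol directs does not fit that choice.
- **Not unique.** Subjects who missed doses for other reasons and have no Week 48 score are also FAS nonresponders outside the per-protocol set. True, but they do not meet the failure criteria the exception was written around.
- **Small group.** The SAP's failure list is mostly tied to psoriasis treatment, so many of these subjects may be stopped for lack of effect and be kept. This stands as a limit on size. Protocol 10.2 nevertheless gives prohibited medication as its own ground and says "The reason for study drug discontinuation must be documented in the eCRF and in source documents", so the reason for stopping will decide who is kept.
- **Not all nonresponders.** A subject stopped for lithium or an antimalarial need not be a treatment failure. Correct; the calculation and the fix concern only subjects who meet Section 5.1.3.1.
- **Consequence.** The testing sequence runs on the FAS, and nothing requires per-protocol success. The primary endpoint has three sensitivity analyses that apply the failure rules without the continuing condition, and discontinuation reasons are tabulated by arm. Under the planned effect the gap is harmless: 75% vs 65% with 1%/3% dropped still gives 8.75 points and a lower bound of 3.2. All of this stands. It limits the importance of the gap but does not remove it.

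**Conclusion.** The concern holds. Read as written, the exception leaves out failures who followed the protocol's default path, so they count against their arm in the FAS and vanish from the per-protocol set. Confidence in the reading is high; the number of subjects affected is unknown.

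The primary test, its Type I error and its power are untouched. For the per-protocol analysis the effect is close to nil if the arms lose equal shares. It becomes material only if they differ and the result lies near the margin: with 3% against 1% dropped, the difference shifts by about +1.1 or -1.6 points at 60% vs 70%. Those shares, the size of the imbalance and the true rates at the margin are assumptions. The last runs opposite to the planning assumption, which favours guselkumab. The point should be corrected because this analysis supports every non-inferiority endpoint and the repair is simple.

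**What to change.** Reconcile the exception in SAP 2.4.1.2 with Protocol 8 and 10.2 by changing the analysis-set wording only. For example: *Any subject whose exposure is incomplete because a Section 5.1.3.1 failure criterion was met before the endpoint stays in the per-protocol set as a nonresponder, including a subject discontinued for starting prohibited medication, irrespective of whether dosing went on.* Tying the rule to Section 5.1.3.1 keeps out stops for drugs that are not treatment failures.

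In the summary of per-protocol exclusions that is already planned, show the reasons by arm and endpoint, so that any imbalance is visible.

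The cost is one SAP sentence and one programming flag before database lock. Concomitant therapies and the reason for stopping study drug are already collected. No change to the clinical stopping rule is proposed.
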